Telephone Risk Assessments. Risk assessment will be conducted with all participants during the initial eligibility screening. Elements of risk assessment will include level of suicidal ideation and suicidal intent, using questions from the University of Washington Risk Assessment Protocol (UWRAP). If the Veteran endorses either of these items, further questions will be asked, including presence and level of specificity of a plan, access to weapons and other means, presence of known risk factors (e.g., recent loss, substance misuse, chronic pain or other serious medical problems), and presence or absence of deterrents. The PI will be notified of all such occurrences immediately. Following the procedures of the Bedford VA, if a Veteran is at imminent risk of suicide at the time of a phone screen, the psychology technician will direct the Veteran to [name], or their clinician designee via warm telephone transfer. The psychologist will conduct a suicide risk assessment over the telephone in order to determine the Veteran's level of risk. If the psychologist deems the Veteran to be at imminent risk, s/he will call the police and request emergency services via a warm transfer. The psychologist will stay on the line with the Veteran until s/he makes contact with emergency services and care is transferred. In the unanticipated event that a licensed clinical psychologist is not available, and study staff are unable to reach the emergency room at the VA, they will conduct a warm transfer to the Veterans' Crisis Line. If they believe that the Veteran is not at imminent risk, but may need a welfare check, s/he will coordinate with VA police and the suicide prevention team. We will coordinate with credentialed, clinical research staff at each study site to ensure that there is constant coverage by a licensed clinical psychologist. As necessary, the study team will collaborate with the local suicide prevention coordinator to facilitate care and clinical follow-up. If a potential participant is hospitalized, they will remain potentially eligible and will be invited to participate during or after their hospitalization.

Face-to-Face/Telehealth Assessments. The Columbia Suicide Severity Rating Scale will be used to assess and address any potential risk associated with participating in the study at each assessment session (i.e., baseline, midpoint, etc.). Using results from this measure, study staff will be trained to immediately evaluate responses the Columbia and respond accordingly to the standard operating practice we have implemented in the protocol should the participant requires immediate crisis intervention (see below).

Research Sessions. All research staff will complete VA required research trainings. Study staff will contact [name] or their clinical designee if other concerning information regarding the participant's safety or the safety of others is identified during administration of the protocol. Study staff will have emergency contact information available at all times for the PI or designee, as well as crisis management and emergency services (e.g., VA National Veterans Crisis Line, Psychiatric Emergency Services, 911).

If contacted, [name] or her clinical designee will conduct a more thorough risk evaluation and will initiate appropriate follow-up procedures. Follow-up procedures for high risk are detailed below:

- *High Risk Procedure.* If a participant is judged by [name] or her clinical designee to be at imminent suicide risk during treatment sessions, the participant will be escorted to the Bedford VA Mental Health Walk-In Clinic for evaluation of risk and potential need for hospitalization. In order to ensure the safety of the participant, we will ask the participant to provide contact information for themselves and 3 other parties who 1) know how to get in contact with the participant, and 2) the participant gives consent for study staff to contact. If the participant does not show up for an appointment, we will contact them. If we cannot reach the participant repeatedly, we will attempt to get in touch with the contacts the participant has provided. If we still cannot reach the participant, study staff will coordinate with the suicide prevention team to locate the participant and ensure their safety. Participants will be made aware of these procedures at the start of the study.

4.6.2 Data and Safety Management Plan:

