(SCID-5) to assess for potential psychosis, substance use disorders, or clinically-significant suicidality. Eligible subjects will then complete self-report measures. Participants with additional, co-morbid pain diagnoses will not be excluded. Data will be collected at baseline, the study midpoint (approximately 3 weeks), end of treatment/7 weeks, and at the one-month follow-up period. Self-report baseline and post-baseline assessments will be administered either in-person or online by Qualtrics, a VA-approved platform and vendor. Length of time for assessments will take approximately 2 hours for baseline assessments, 1.5 hours for the mid-point survey, approximately 2 hours for the 7 week/post-intervention surveys, as well as approximately 1 hour for the 1 month follow-up surveys. See Table 2 for the measurement schedule:

Table 2: Measurement Schedule for Phase 3

MEASURE	BASELINE	MIDPOINT	INTERVENTION END /7 WEEKS	1-MONTH FOLLOW- UP
Demographics	X			
MEAQ	x		x	x
CPVI	x	x	x	x
PHQ-9	x	x	x	x
VR-36	x	x	x	x
POQ-SF	x	x	x	x
SCID-5	x			
BPI	x			
CPAQ	x	x	x	x
Usability survey*			x	
SUS*			x	
WAIS-S*			x	
CSQ-8*			x	
Qualitative Interview			x	

*will only be assessed in invention group

Demographics, functional health, and pain measures.

Demographic measures will include age, gender, race and ethnicity, and education. We will also include questions related to medications currently being used for the management of physical or psychological conditions, self-reported using a single-item listing diagnoses, and at baseline and 7 weeks conduct a CPRS record review for such information. These measures will take approximately 10 minutes.

Feasibility and

Acceptability Measures: Feasibility outcomes will include recorded information on recruitment rates, retention rates within each condition, measure completion rates, how often Veterans access the website, and any reported problems with the website. This information will be collected by the research team.

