Phase Three: We will aim to recruit up to 60 participants over fifteen months total to allow for the desired final 40 participants screened as eligible and randomized into the pilot RCT study, specifically aiming for recruiting 3-4 participants per month. Subjects for the proposed study will be recruited over the course of approximately 15 months and be screened according to their presence of chronic pain and other inclusion/exclusion criteria. First, potential participants will be pre-screened by phone to determine whether basic study eligibility criteria are met. Individuals who remain eligible after the phone pre-screen will be randomized in a 1:1 ratio. Veterans randomized to VACT-CP will receive 7 online-module based weekly sessions of treatment via personal computer or provided laptop with wireless accessibility at the Bedford VAMC. Veterans in the waitlist control will be provided with a list of common pain resources at the Bedford VAMC. Subjects will be paid \$60 for the baseline assessment, \$40 at the midpoint testing visit/week 3 for waitlist control, and, \$60 for the end of treatment (Session 7)/end of week 7 for control group participants and \$40 for a one-month follow-up (total; \$200 total).

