4.4 Inclusion/Exclusion Criteria

Phase One:

Inclusion Criteria

- 1) Currently working at the VA Bedford Healthcare System or one of its affiliated CBOCs in a clinical capacity, including mental health, physicians, nursing, pharmacists, or primary care/behavioral health staff
- 2) Currently seeing Veterans to assist in their management of chronic pain

Exclusion Criteria.

- 1) Any cognitive or physical impairment that would interfere with study participation of using a computer and providing verbal feedback.

Phase Two:

Inclusion Criteria

- 1) Current diagnosis of non-cancer chronic pain
- 2) Competent to provide written informed consent
- 3) Ages 18 and older
- 4) Access to the internet at least weekly through a computer

Exclusion Criteria

- 1) Any cognitive or physical impairment (e.g., auditory or sight issues issues) that would interfere with study participation of using a tablet/computer and providing feedback.

Phase Three:

Inclusion Criteria

- 1) Current diagnosis of non-cancer chronic pain, defined as 1) at least one pain-related diagnosis indicated by an ICD-9 or -10 code related to either Musculoskeletal pain or Joint Problems/Osteoarthritis or 2) presence of chronic pain of at least mild to moderate severity as indicated by two or more NRS pain scores of ≥ 4 at three separate VA outpatient visits in past year based on a CPRS record review;
- 2) Has a working, high-speed wireless internet connection at home, or is willing to access sessions either at the Bedford VAMC by using a provided laptop in a secure space
- 3) Competent to provide written informed consent
- 4) Ages 18 and older.

Exclusion Criteria

- 1) Any current or lifetime DSM-5 psychotic disorder
- 2) Current or recent (within 1 month of study entry) DSM-5 alcohol or drug use disorder
- 3) Current use of any other chronic pain-related behavioral or psychological treatment
- 4) Any cognitive impairment that would interfere with study participation
- 5) Clinically significant suicidality within the past year
- 6) Presence of any clinical features requiring a higher level of care (inpatient or partial hospital treatment)
- 7) Any cognitive or physical impairment that would interfere with study participation of using a laptop/computer and providing feedback]

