6) The Bedford VA has institutional policies requiring all clinical investigators and their key personnel to undergo mandatory training in human research participant's participation. The program includes all clinical researchers regardless of their source of funding. Researchers typically fulfill this requirement by completing Bedford VA research trainings. All research staff have successfully completed education in human subjects research through the Bedford VA.

Phase Three: To protect Veterans against risk, the same steps as Phase 2 will be followed. In addition, we will take the following steps during the research process:

- 1) Potential study participants will be screened initially over the phone for eligibility. For screening purposes only, this study will maintain a contact log. This log will contain the identifying information for veterans who are identified by research staff via medical record review or who contact research staff after learning about the study. It will contain the veteran's name, social security number, contact information, and status (No Response, Screened In, Screened Out, Pending, Chose not to participate). This log will be password protected and stored on a VA shared drive. This log will be maintained until the end of the recruitment period in order to prevent ineligible or uninterested veterans from being contacted again by letters from providers or by research staff. The identifiable information will be used only by members of the research team. This information will not be disclosed to anyone outside the VA. The proposed study poses minimal risk to the privacy of the subjects because all data will be stored on secure servers, the intervention website (VACT-CP) will not collect any PII or PHI, and all assessments will take place using a secure space at the VA, our VA-approved Qualtrics system for surveying participants, or using a VA-approved secure teleconferencing system (MS Teams, Cisco, WebEx, phone calls, etc). Study screening forms will be coded, and will not contain the veteran's name, social security number, or date of birth. All identifying information will be maintained in locked file cabinets in locked offices or on a VA Shared Drive.

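### The Phase 3 telephone risk procedure directs staff to invite hospitalised callers, which conflicts with exclusions 5 and 6 during a suicide-related admission and with exclusion 5 for 12 months afterwards

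*Combined protocol and SAP*

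**What the plan says.** Section 4.6.1 lists protective steps by phase. The Phase 3 part opens with "Phase Three: To protect Veterans against risk, the same steps as Phase 2 will be followed" and then adds further steps. The paragraph headed Telephone Risk Assessments comes under these additions. It states that "Risk assessment will be conducted with all participants during the initial eligibility screening", sets out the emergency transfer to be used "if a Veteran is at imminent risk of suicide at the time of a phone screen", and closes with the sentence at issue: "If a potential participant is hospitalized, they will remain potentially eligible and will be invited to participate during or after their hospitalization".

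Section 4.4 gives the Phase 3 exclusions. Number 5 is "Clinically significant suicidality within the past year". Number 6 is "Presence of any clinical features requiring a higher level of care (inpatient or partial hospital treatment", closing the bracket there. Neither carries an exception for a caller admitted after the risk screen.

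Step 1 of the same Phase 3 list in section 4.6.1 sets up a contact log with status codes. Its stated purpose is to keep Veterans who are ineligible or not interested from being approached again.

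**The concern.** The risk procedure and the exclusion list give staff opposite instructions about the same caller. A staff member working from section 4.6.1 would invite the person, possibly while still an inpatient. One working from section 4.4 would record an exclusion and make no further approach.

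These are the callers at highest risk, and Phase 3 offers either a self-guided online programme or a wait list with a sheet of pain resources (section 3.3). How such callers are counted would also depend on which section was followed. Aim 3c in section 3.5 uses exclusions to judge whether a criterion needs to be re-examined.

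**Working it through.** The plan states no figure here, so the check is mainly a comparison of texts.

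**Which phase.** Phase 2 has no suicidality or level-of-care exclusion, so the sentence would cause no conflict there. Its place among the additional Phase 3 steps makes it a Phase 3 rule.

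**Assumptions.** (a) The admission is suicide-related. The sentence gives no reason, but it closes a paragraph wholly about suicide risk and emergency transfer. (b) Such an admission counts as clinically significant suicidality, a term that section 4.4 does not define.

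**Branches under these assumptions.**

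| Time of invitation | Exclusion 6 (inpatient-level need) | Exclusion 5 (past year) | Conflict? |
|---|---|---|---|
| During the stay | Met | Met | Yes, with both |
| After discharge, under 12 months from the episode | May have lapsed | Met | Yes, with 5 |
| After discharge, 12 months or more from the episode | May have lapsed | No longer met by this episode | None from this episode |

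**Reach of the 12-month look-back.** Section 4.1 says "Subjects for the proposed study will be recruited over the course of approximately 15 months". A caller whose episode falls at month *t* of recruitment clears the look-back no earlier than *t* + 12. To be invited validly before recruitment closes requires *t* + 12 ≤ 15, so *t* ≤ 3. Only callers screened in about the first 3 months can qualify: 3/15 = 20% of the window. The other 12/15 = 80% cannot. Reading these as shares of callers assumes steady screening, which fits the section 4.1 target of 3 to 4 recruits a month.

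**Contact log.** Under section 4.4 the caller is ineligible, and the log exists to prevent another approach. Under the telephone procedure the caller is approached again. The log has a Pending code, but nothing says whether it covers this case.

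**Checks after the invitation.**
- Section 3.4: at the baseline assessment staff confirm eligibility and give the SCID-5 "to assess for potential psychosis, substance use disorders, or clinically-significant suicidality".
- Section 4.5.2: enrolment follows consent only if the criteria are met. The plan expects 2 of every 3 consented to qualify: 60 × 2/3 = 40, so up to 20 are expected to fail.
- Section 4.6.1: the Columbia scale is given at each assessment, as a safety measure.
- Against these, section 4.1 moves people who pass the phone pre-screen to 1:1 randomisation with no step named in between, and section 4.5.1b randomises remote participants after verbal consent.

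**Size if one such person were randomised.** 1/40 = 2.5% of the sample, or 1/20 = 5% of an arm. This is conditional on passing every check above. The documents give no rate of hospitalisation after screening.

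**The case against.** The strongest reply is that an invitation is not enrolment. The sentence says only that the person stays potentially eligible. It does not waive section 4.4, and an invitation followed by an eligibility check fits that wording. The baseline confirmation, SCID-5 and enrolment condition are real safeguards. The plan also monitors suicide risk in both arms, with staff assessments at weeks 3 and 6, safety plans where needed and a high-risk procedure.

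Much of this stands. A reader might infer that the plan would randomise people hospitalised for suicide risk. The documents do not support that: three sections place checks in the way, although section 4.1 leaves their order relative to randomisation unclear. A reader might also infer that the sentence contradicts both exclusions at all times. It does not: exclusion 6 concerns present need and bears on the stay itself, exclusion 5 lapses after a year, and an admission for another reason need not breach exclusion 5 at all.

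Nor does the text support a claim that feasibility results would be materially distorted. Section 3.4 does not list an exclusion rate among its feasibility outcomes. The link is only through the criterion review in Aim 3c, and the Aim 3a usability analyses are not shown to be affected.

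What the reply does not answer is the instruction to approach. Staff are told that the person will be invited, including while in hospital, at a time when section 4.4 already rules the person out. A later check does not reconcile those two instructions, and neither does safety monitoring.

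**Conclusion.** This is an internal inconsistency, wrong as written. For a suicide-related admission, the invitation during the stay conflicts with exclusions 5 and 6. The invitation after discharge conflicts with exclusion 5 for 12 months, which leaves roughly the first 3 months of a 15-month window in which a caller could later be invited validly. It also conflicts with the purpose of the contact log if the caller is logged as ineligible.

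The conclusion rests on reading the sentence in its suicide-risk context and on treating such an admission as clinically significant suicidality. The number of people affected is unknown and probably small, and any effect on the exclusion counts reviewed under Aim 3c is likely minor. The case for correction rests on participant safety and on staff having one instruction to follow, not on a statistical effect.

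**What to change.** Reconcile the Phase 3 exclusions in section 4.4 with the contact-log step and the Telephone Risk Assessments paragraph in section 4.6.1, so that one eligibility and re-contact rule covers a person hospitalised after a risk screen. State whether the sentence refers to suicide-related admissions, to others, or to both. Carry the rule into the Phase 3 phone-screen script, and say which log status such a caller receives, so that exclusions are counted the same way by all staff. Which clinical rule applies is for the study clinicians to decide.

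The cost is about one sentence in section 4.4 or 4.6.1, plus matching edits to the script and log codes. It needs no extra participants or procedures.

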4.6.2.1 Data Security

How/where informed consent documents and study data will be stored:

All data collected for recruitment and for screening purposes will be filed separately from any potential identifying information for each subject. All data will be filed securely under lock and key in file cabinets at the Bedford VA Hospital (Building 5, Room 135b). Data files related to study participation, including participant data and informed consent documents, will be stored directly on a VA-secure server designated for this study only by anonymous subject study number, will be securely maintained, and will be assessable only to research staff directly involved in this project. Upon completion of the study and data entry and analysis, all data and files will be stored and archived indefinitely under lock and key, or on the designated secure server. All hard-copies of non-sensitive study documents will be secured in locked file cabinets within locked SoCRR (Social & Community Reintegration Research) offices in Building 5 (Room 135b) at the Bedford VAMC.

Electronic files and data will be de-identified and labeled with the study ID number, and then stored in a password-protected file on a VA server folder (<\\R04BEDNAS21.v01.med.va.gov>) (specific to this study). Storage will be in accordance with VA Research Data Security and Privacy requirements. De-identified data will be labelled only with a non-identifying study subject number. Data files will be securely maintained, and will be accessible only to research staff directly involved in this project. All video recordings will be stored on the server and accessible only to study personnel for fidelity monitoring purposes.

De-identified questionnaire data for this study (if not collected by Qualtrics) will be stored in a database called REDCap (Research Electronic Data Capture), which is housed on a VA-secured, VA Informatics and Computing Infrastructure (VINCI) server at the Austin Information Technology Center (AITC). To ensure the protection of Veteran data, VINCI maintains compliance with the guidelines set forth by Veterans Health Administration (VHA) Handbook 1200.12, Use of Data and Data Repositories in VHA Research, and all other applicable VA and VHA policies and regulations. In addition, VINCI has undergone all security certification activities in support of obtaining an Authorization to Operate (ATO). Access to VINCI resources are approved in accordance with the requirements of National Data

Systems (NDS), VHA Handbook 1200.12, Use of Data and Data Repositories in VHA Research, and all other applicable VA and VHA policies and regulations. All data transferred from VINCI is subject to audit for compliance. VINCI has multiple layers of security and disaster recovery to prevent data loss. Study data is kept in accordance with the Department of Veterans Affairs Record Control Schedule 10-1 (RCS 10-1). REDCap is only accessible via a VA network connection and via a VA-secured computer.

For Phase 3, participants will have the choice to complete assessments in person at the Bedford VAMC, via a telephone call with staff, or online via VA-FedRAMPs approved, HIPAA compliant Qualtrics platform. If participants choose this option, this data will initially be collected and stored on the Qualtrics platform. At the close of the data collection period, all data will be transferred to a VA-secure share drive accessible only to approved research staff. Transfer will occur using a direct download using a VA-secure computer and behind the VA firewall. This data will be downloaded and stored (download will be FIPS 140-2 compliant and data will be fully de-identified in accordance with HIPAA deidentification standards) on an encrypted VA server in password protected files on our secure VA server space that is designated and accessible for this study only.

The collected data will contain PHI but will be de-identified. All the data collected will remain in an electronic folder that can only be accessed by the research team who are identified on the protocol submitted to the IRB. Access to the study data on the VA server will be restricted to the members of the research team, where each research team member will have their own username and password. Upon completion of the study and data entry and analysis, all data and files will be stored and archived indefinitely under lock and key, or on the designated server and the REDCap database.

Procedures to ensure the *privacy of subjects*:

Phase 2: Subjects will be screened via a private phone call, and usability testing sessions will be conducted using Skype/Cisco, which is a secure VA approved platform for communication with Veterans. Veterans will be asked to complete all phone and Skype/Cisco communications in a secure room, alone, with the door closed.

Phase 3: Subjects who request to complete study activities (assessment, online website use) at the Bedford VAMC will be asked to come to the PI's program offices, which are located in Building 5, away from busy patient areas. Use of the website (VACT-CP) and any study questionnaires will be completed in the PI's program offices, with the door closed. A white-noise machine will be used to ensure that information from the subject will not be heard outside of program offices.

Procedures to maintain the *confidentiality of data/information*:

All data will be used specifically for the research purposes described in this application. No identifying information will be associated with any information obtained from questionnaires or interview data, including names, addresses, or phone numbers. All data will be kept in accordance with VA regulations. Each participant in the study will be assigned an arbitrary study number at random and this number will be used for all data for subsequent analyses. All data are filed securely under lock and key in file cabinets at the VA Bedford Healthcare System (in Building 5). Upon completion of the study and data entry and analysis, all deidentified data and files will be stored and archived indefinitely under lock and

key. All computers are password-protected. All audio files will not contain identifiers and will be downloaded after being recorded to password-protected files on VA computers. Information will not be made available to any party without the written informed consent of the subject and at the subject's request.

How/where data will be stored (location with room number):

Data will be stored in locked file cabinets in Building 9, a Bedford VA building that is locked during non-business hours. Computerized data files will be stored in password-protected files on a secure VA server designated for this study, and accessible by study staff, only. For Phase 3, participants will have the choice to complete assessments in person at the Bedford VAMC, via a telephone call with staff, or online via VA-FedRAMPs approved, HIPAA compliant Qualtrics platform. Data that is collected in person or by phone will be input to RedCAP. If participants choose the Qualtrics (online survey) option, this data will initially be collected and stored on the Qualtrics platform. At the close of the data collection period, all data will be transferred to a VA-secure share drive accessible only to approved research staff. Transfer will occur using a direct download using a VA-secure computer and behind the VA firewall. This data will be downloaded and stored (download will be FIPS 140-2 compliant and data will be fully de-identified in accordance with HIPAA deidentification standards) on an encrypted VA server in password protected files on our secure VA server space that is designated and accessible for this study only.

The collected data will contain PHI but will be de-identified. All the data collected will remain in an electronic folder that can only be accessed by the research team who are identified on the protocol submitted to the IRB. Access to the study data on the VA server will be restricted to the members of the research team, where each research team member will have their own username and password. Upon completion of the study and data entry and analysis, all data and files will be stored and archived indefinitely under lock and key, or on the designated server and the REDCap database.

Who will have access to the data/codes:

Only [name] and authorized study personnel will have access to the data/codes. Once a research staff member is no longer working on this protocol, they will no longer have access to data and codes.

What will happen to the data when the research is complete:

All data will be kept in accordance with VA regulations. Upon completion of the study and data entry and analysis, all deidentified data and files will be stored and archived indefinitely under lock and key.

How data will be archived:

The data will be archived. Data will be archived on VA authorized storage media on the VA server, and hard copies of data (i.e., questionnaires and interview data) will be stored in locked file cabinets in Building 5, Room 135b.

Will data with identifiers be released?

Data with identifiers will not be released, transferred, or shared.

Coordination with Other Sites

How/where data will be stored:

All participant website usage data in the lab will be managed by Northeastern University under the guidance of [name], the lead for the creation of the VACT-CP online program. **No PHI or PII will be transmitted to or from Northeastern University.**

Numerous safeguards will keep electronic and hard copy data secure. Each subject will be assigned a code number so that, should any non-study personnel gain access to the data, they will not know to whom they belong. Only study staff associated with the VACT-CP study will have access to these codes. All hard copy data will be kept in a locked file cabinet accessible only by authorized research staff approved this study. A secure password is required to access computers at each site, and computer networks are on secured servers that meet or exceed federal confidentiality standards.

All connections to the VACT-CP website will be made using the secure sockets layer (SSL).

Participant usage data are maintained on a server in a locked server room at Northeastern University. Full access to the server is restricted to two staff members of Northeastern University.

There is deidentified data from the website that includes information about engagement in the website (e.g. Veteran responses to Coach Anne questions, time spent on the website, etc), but no clinical information per se that will be accessed by Northeastern University for analysis. **Northeastern University will not have access to patient usability testing data that is recorded for Phase Two or Phase Three.**

What will happen to the data when the research is complete:

All data will be kept in accordance with VA regulations. Upon completion of the study and data entry and analysis, all de-identified data and files will be stored and archived in accordance with VA regulations.

How data will be archived:

The data will be archived. As mentioned above, any hard copy data will be archived on VA authorized storage media and hard copies of data (i.e., questionnaires and interview data) will be stored on the VA server or in locked file cabinets in Building 5, Room 135b. However, de-identified digital site usage data will be archived in accordance with VA regulations by Northeastern University.

Will data with identifiers be released?

Data with identifiers will not be released, transferred, or shared by Northeastern University, as they will not have any PHI or PII.

We will retain a complete record of all data obtained during the VA portion of the research in accordance with privacy requirements, the Federal Records Act, and VHA Records Control Schedule

(RCS) 10-1. All disclosures and data transmission will meet privacy and security requirements per VA Directive 6500, VA Handbook 6500, and VHA Handbook 1605.1.

All of the above listed practices are designed to minimize risks to subjects while being consistent with sound research design. Furthermore, the risks are reasonable in relation to anticipated benefits.

